5.1.2.6 Japanese criteria of CAL

The primary analysis (Section 5.1.1) was repeated using the Japanese Ministry of Health and Welfare criteria for CAL⁴, defined as follows:

- In children <5 years, any coronary artery diameter ≥ 3 mm; in children ≥ 5 years, ≥ 4 mm;
- Or ≥ 1.5 times the diameter of an adjacent segment.

5.1.2.7 Z threshold ≥ 2.5 for CAL

The occurrence of CAL was re-defined as a z score ≥ 2.5 in any of the LMCA, LAD, LCX, or proximal/middle RCA segments. The same statistical method as in Section 5.1.1 was used.

5.1.2.8 CAL defined based on LAD and proximal RCA

The occurrence of CAL was re-defined as a z score ≥ 2 in either the LAD or proximal RCA segment. The same statistical method as in Section 5.1.1 was used.

5.1.2.9 Adjusting for the baseline maximum z score

Using the same method as in Section 5.1.1, this sensitivity analysis adjusted for the maximum z score at baseline instead of the mean of 5 coronary artery baseline z scores.

5.1.2.10 GLM model analysis

This analysis used generalized linear model (GLM) treating response variable as a simple binary outcome without adjustment for any covariate. RD and 95% CI were estimated using a binomial distribution and an identity link function.

Sensitivity analyses 5.1.2.3 – 5.1.2.7 were conducted during manuscript preparation, and analyses 5.1.2.8 – 5.1.2.10 were added in response to reviewers' suggestions during manuscript revision.

5.1.3 Subgroup analysis of the primary outcome

Subgroup analyses will be performed for the primary outcome using GEE model as the primary analysis. We will stratify the analysis by age group (disease onset age ≤ 1 or > 1 year), gender (male or female), BMI group (according to different BMI distributions of age and gender in Chinese children, BMI will be stratified into three groups, underweight, normal weight, and overweight and obese, BMI percentile for age and gender of P10 and P85), complete or incomplete KD, IVIG respond or not and CAL presence or not at baseline. Same strategy and methods will be used as described in section 5.1.1.

Same strategy will be used when sensitivity analysis is performed for the secondary outcomes.

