5.1. Primary Outcome Analysis

5.1.1 ITT analysis of the primary outcome - the primary analysis

The primary analysis will be based on the ITT population as defined above. The primary outcome is a binary outcome: CAL occurs or not within 1 month of illness onset. Since CAL will be repeatedly examined at enrollment, 2 weeks, 1 month, 3 months, 6 months and 12 months respectively, generalized estimating equation (GEE) model will be performed, with treatment, visit and interaction between treatment with visit as fixed effect, patient ID as cluster effect, the mean of 5 coronary artery baseline z scores (described in section 2.2.1) as covariate variable. Risk difference (RD) and two-sided 95% confidence intervals (CI) between the two treatment groups will be estimated from the model using a binomial distribution and identity link function. OR with 95% CI at each time point will be obtained using GEE model with binomial distribution and logit link function. Binomial distribution and log link function will be used to obtain estimation of risk ratio (RR) and 95% CI. Exchangeable correlation structure is assumed for within-group variation for all the GEE models. The P value for the interaction term will be used to determine the statistical significance of the group difference at specific time point.

If the above GEE model does not converge, a poisson distribution will be used for the family function. A negative binomial distribution will be subsequently used for family function in case the GEE model based on poisson distribution does not converge. RD, OR and RR with their 95% CI

estimates will be reported by using identity, logit and log link function, respectively. In the final analysis, a normal family distribution was used because none of the three prespecified distribution models converged. RD and 95% CI estimates were derived using identity link function.

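### The subgroup section repeats the primary GEE within strata of six factors but specifies no treatment-by-subgroup comparison and no rule for interpreting the results

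*SAP*

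**What the plan says.** SAP section 5.1.3 opens with "Subgroup analyses will be performed for the primary outcome using GEE model as the primary analysis". It then names the factors: "We will stratify the analysis by age group" (two levels, split at one year), by gender (two levels) and by BMI, where "BMI will be stratified into three groups, underweight, normal weight, and overweight and obese", followed by "complete or incomplete KD, IVIG respond or not and CAL presence or not at baseline". It closes with "Same strategy and methods will be used as described in section 5.1.1".

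The model imported from section 5.1.1 is a GEE "with treatment, visit and interaction between treatment with visit as fixed effect", plus the mean of the five baseline z scores as a covariate. Section 5.1.1 uses the P value of that treatment-by-visit interaction to decide whether the arms differ at a given time point.

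The shell of Table 3 (section 6.2) gives a risk difference, odds ratio and risk ratio with 95% CI for each stratum and visit. It lists age, gender and BMI only, which is 7 of the 13 strata named in the text, and has no column that compares strata. No section of the SAP states a treatment-by-subgroup term, a heterogeneity test, or how subgroup results are to be read.

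**The concern.** A subgroup analysis asks whether the treatment effect differs between kinds of patient. The planned output gives the effect in each kind of patient separately and stops there. Applying the section 5.1.1 rule inside a stratum produces a verdict of significant or not for that stratum. Two such verdicts placed side by side do not test whether the effects differ.

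The trial is sized for one comparison in the whole sample. Every stratum is therefore underpowered, and strata of unequal size have unequal power. Even under a uniform effect, the larger stratum will often reach significance while the smaller does not. With no planned comparison and no interpretation rule, such a pattern could be reported as prednisolone working in one group and not in another.

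**Working it through.** **Inputs**

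- CAL at one month 12.4% (control) vs 9.1% (experimental), α = 0.05, power 0.80, 1,400 per arm: SAP section 3.5. Tests are two-sided: section 6.
- Factors and levels: section 5.1.3.
- Stratum shares are not given. Assumed here: 50/50 to 10/90 for two-level factors.
- Assumed: the same CAL rates in every stratum, and a simple one-month comparison of proportions in place of the GEE, without the baseline covariate.

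**1. Number of strata.** Age 2, gender 2, BMI 3, KD type 2, IVIG response 2, baseline CAL 2: 2 + 2 + 3 + 2 + 2 + 2 = 13. The Table 3 shell shows 2 + 2 + 3 = 7.

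**2. The plan's own sample size.** The usual two-proportion formula with pooled variance under the null gives 1,382 per arm, and power at 1,400 per arm is 80.5%. The stated 1,400 reproduces.

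**3. Power within a stratum under a uniform effect.** Let v = 0.124 × 0.876 + 0.091 × 0.909 = 0.1913. With n per arm in the stratum, SE = √(v/n) and power ≈ Φ(0.033/SE − 1.96). At an even split n = 700, SE = 0.01653, 0.033/0.01653 = 1.996, and power is 51%.

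**4. Chance that the two strata disagree on significance.** The strata of one factor contain different children, so their results are independent. With powers π₁ and π₂, the chance is π₁(1 − π₂) + π₂(1 − π₁). At an even split this is 2 × 0.514 × 0.486 = 0.50.

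| Split | Power, smaller / larger stratum | Strata disagree |
|---|---|---|
| 50/50 | 51% / 51% | 50% |
| 30/70 | 34% / 66% | 55% |
| 20/80 | 24% / 71% | 61% |
| 10/90 | 15% / 76% | 69% |

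For a three-level factor such as BMI, with assumed shares of 10/75/15, the chance that the three strata do not all agree is 76%.

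**5. The same situation with a direct comparison.** A two-sided 5% test of the difference between the stratum risk differences signals heterogeneity falsely in 5% of trials per factor, whatever the split.

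**6. What that test can detect.** SE of the difference = √(v/n₁ + v/n₂). At 50/50 this is √(2 × 0.1913/700) = 0.0234. Power for a true 3.3-point difference is Φ(0.033/0.0234 − 1.96) ≈ 29%. The difference detectable with 80% power is 2.80 × 0.0234 ≈ 6.6 points. At 10/90 the figures are about 14% and 10.9 points.

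**7. Several factors.** With five unadjusted tests, treated as independent, the chance of at least one false positive is 1 − 0.95⁵ = 23%.

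**The case against.** The best defence is that the planned output already permits the comparison. The strata of one factor are disjoint, so a reader can take the difference of two risk differences and recover its standard error from the two confidence intervals. Table 3 shows intervals and no P value. This stands in part: the information is there, but the comparison is neither prespecified nor reported.

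The size is also soft. Stratum shares are assumed, and equal CAL rates are implausible for the baseline-CAL strata, since that factor is closely tied to the outcome. The percentages therefore illustrate the risk and do not predict this trial's results.

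The remedy has limits too. Section 5.1.1 reports that the binomial, Poisson and negative binomial models all failed to converge, and a three-way model is larger. The interaction test also has little power. Both points are fair and shape the fix. Low power is no reason to omit the comparison, because the stratum results are underpowered as well and answer a different question.

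Four stronger readings are tempting, and the document does not support them:

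- *The plan will judge subgroups by comparing significance.* No text says so; the plan leaves that reading open. Separate fits per stratum are themselves inferred from the wording of section 5.1.3 and the Table 3 layout, although that is the natural reading.
- *Who benefits is a question this trial set out to answer.* The Introduction mentions that debate as background. No objective in section 2.1 concerns subgroups, and section 5.1.3 has no stratum for baseline risk of IVIG resistance.
- *Thirteen strata carry a 49% chance of a false positive.* That figure, 1 − 0.95¹³, needs 13 independent tests. These are six partitions of the same children, so the tests overlap.
- *One added term repairs it.* A three-way model also needs all the lower-order subgroup terms.

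**Conclusion.** The point holds as an analysis gap that should be corrected. Section 5.1.3 fixes a subgroup method that cannot test effect modification, and nothing elsewhere in the SAP supplies the missing comparison or a rule for interpretation. Under a uniform 3.3-point effect, strata of a two-level factor would disagree on significance in about 50% of trials (even split) to 61% (20/80), against 5% per factor with a direct test. This rests on the section 3.5 rates, 1,400 evaluable per arm, assumed stratum shares, equal rates across strata and a one-month approximation to the GEE. The primary estimate, its error rate and its conclusion are untouched; only subgroup claims are at risk.

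**What to change.** For each of the five baseline factors (age, gender, BMI, KD type, baseline CAL), report the between-stratum difference in the 1-month risk difference with its 95% CI and P value, in one of two ways:

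- as the 1-month contrast from one model with treatment × visit × subgroup and all lower-order terms. The contrast must be named, because the two-way treatment-by-subgroup coefficient alone refers to the reference visit;
- if that model does not converge, from the independent stratum estimates: D = RD₁ − RD₂, SE(D) = √(SE₁² + SE₂²).

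BMI has three levels and needs two contrasts with a joint 2-df test. Add the comparison as a column in Table 3, and list there all the factors that the text names. State that subgroup findings are exploratory and that no claim of a differential effect is made without this comparison.

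Report IVIG response separately. Section 3.3.1 defines resistance by fever after the initial infusion, so it arises after randomization and may itself be affected by treatment. Present it as a descriptive stratification and not as effect modification.

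Cost: no new data. With V visits in the model, a two-level factor adds 2V parameters and BMI adds 4V. Five unadjusted tests carry about a 23% chance of at least one false positive if independent, and power is low, so the reading stays exploratory. Because section 5.1.1 already reports what was done in the final analysis, a comparison added now should be labelled as added afterwards.

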5.3 Handling of Missing data	16
6. General Considerations for Data Analyses.....	16
6.1 Data Summaries	16
6.2 Graphical Displays	17
7. Study Variable List.....	21
8. Reference.....	38

1. Introduction

Kawasaki disease (KD), an acute systematic vasculitis, has been reported worldwide nowadays and more prevalent in Asia. Coronary artery lesion (CAL) is the most important complication and one of the main predictors to the long-term prognosis of KD. CAL can induce coronary artery aneurysm (CAA), occlusion, myocardial ischemia, myocardial infarction and even death, making KD a major cause of the acquired heart diseases in children. The large dose of intravenous immunoglobulin, together with aspirin (abbreviated as IVIG treatment) administered during the acute phase of KD has been well proved in reducing the occurrence of CALs. Given certain proportion of patients response poorly to this treatment, which is commonly linked with higher risk of CAL, it is worth exploring whether more aggressive treatments are able to achieve better effectiveness in reducing the incidence of CAL or not. Corticosteroid, preferred in the treatments of majority of vasculitis, remains controversial in the acute phase treatment of KD. Several studies suggest that the therapy time, regimen and the targeted people require careful considerations in the corticosteroid's treatment in KD. It is still under arguing that using corticosteroids in the initial treatment benefits all the KD patients rather than those with higher risk of IVIG resistance.

The purpose of this Statistical Analysis Plan (SAP) is to define the outcome variables, statistical methods and analysis strategies for a multicenter open-label randomized controlled trial. The trial aims to evaluate the effects of two therapies in reducing the incidence of CAL for children with acute KD: conventional IVIG treatment plus prednisolone (the experimental arm) and only IVIG treatment (the control arm).

2. Study Objective and Outcomes

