2.1 Study Objective

This is a superiority randomized controlled trial, aiming to provide high quality evidence for

supporting effects and safety of current treatment combining steroid (corticosteroids) in the IVIG treatment plan for newly onset Kawasaki disease pediatric patients. The primary objective is to evaluate the hypothesis that IVIG treatment plus prednisolone will reduce the incidence of CAL at 1 month of illness comparing with the conventional IVIG treatment. The secondary objectives include comparing the need of additional treatment or not and duration of fever after initial treatment, occurrence of CAL after 1 month of illness onset, changes in laboratory data between two treatment groups, and serious adverse events.

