2.2.2 Secondary Outcomes

- 1) Changes in z score of LMCA from admission. Data will be measured at six time points of illness: enrollment, 2th week (± 2 days), 1th month (± 5 days), 3th month (± 5 days), 6th month (± 5 days) and 12th month (± 5 days), respectively.

(Time Frame: from admission to 12 months of illness) (Type: repeatedly measured continuous

variable)

2) Changes in z score of LAD from enrollment. Data will be measured at six time points of illness: enrollment, 2th week (± 2 days), 1th month (± 5 days), 3th month (± 5 days), 6th month (± 5 days) and 12th month (± 5 days), respectively.
(Time Frame: from admission to 12 months of illness) (Type: repeatedly measured continuous variable)

3) Changes in z score of LCX from enrollment. Data will be measured at six time points of illness: enrollment, 2th week (± 2 days), 1th month (± 5 days), 3th month (± 5 days), 6th month (± 5 days) and 12th month (± 5 days), respectively.
(Time Frame: from admission to 12 months of illness) (Type: repeatedly measured continuous variable)

4) Changes in z score of the proximal segment of RCA from enrollment. Data will be measured at six time points of illness: enrollment, 2th week (± 2 days), 1th month (± 5 days), 3th month (± 5 days), 6th month (± 5 days) and 12th month (± 5 days), respectively.
(Time Frame: from admission to 12 months of illness) (Type: repeatedly measured continuous variable)

5) Changes in z score of the middle segment of RCA from enrollment. Data will be measured at six time points of illness: enrollment, 2th week (± 2 days), 1th month (± 5 days), 3th month (± 5 days), 6th month (± 5 days) and 12th month (± 5 days), respectively.
(Time Frame: from admission to 12 months of illness) (Type: repeatedly measured continuous variable)

6) Need for additional treatment or not. The acute KD patients in both arms resistant to the initial IVIG therapy will be given additional treatment, which will be determined by the prescription record.
(Time Frame: at one month of illness) (Type: binary variable)

7) Duration (hours) of fever (defined as an axillary temperature <37.5 for more than 24 hours) after initiation of initial IVIG among participates of two arms.
(Time Frame: from initiation of initial IVIG infusion to the first record of being afebrile) (Type: time-to-event variable)

8) Change in serum C-reactive protein (CRP) concentration from admission to 72 hours after

completion of initial IVIG infusion.

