3.3 Interventions

3.3.1 Experimental arm: IVIG + Aspirin + Prednisolone

Patients in this arm will receive conventional IVIG treatment plus additional prednisolone 2 mg/kg per day in the initial treatment. The details are as follows:

In both arms, IVIG treatment is administered within 12 to 24 hours with the maximum dose of 60g. The dose of aspirin will be reduced to 3 to 5 mg/kg per day when fever subsides for 3 days and CRP is normal, and continued for at least 6 weeks after onset of KD. If patients resistant to initial IVIG therapy will be given rescue therapy, including a second dose of IVIG (2 g/kg), or a high dose of methylprednisolone (10 to 30 mg/kg per day), or infliximab (5 mg/kg), or other immunosuppressive agents, or a combination with two or more drugs, or even more aggressive treatment such as plasmapheresis, depending on patients' condition and physicians' experience. IVIG resistance is defined as recurrent or persistent fever (axillary temperature $\geq 37.5^{\circ}\text{C}$ or rectal temperature $\geq 38^{\circ}\text{C}$) after 36 hours of completion of initial IVIG infusion.

Patients in the experimental group will additionally receive intravenous methylprednisolone 1.6 mg/kg per day which is given in 2 doses (equal to prednisolone 2 mg/kg, and the maximum dose is 60 mg of prednisolone), then switch to oral prednisolone 2 mg/kg when fever subsides for 3 days. If CRP returns to normal, the prednisolone dose will be tapered over 15 days in 5-day steps, from 2 mg/kg per day to 1 mg/kg per day then to 0.5 mg/kg per day. During corticosteroids administration, 0.5 mg/kg H2-blocker omeprazole will be given per day.

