3.5 Sample Size

This study is a superiority trial. Sample size calculation is performed based on the difference of the primary outcome between the two arms. According to the previous study³, we assume a difference in the proportion of patients with CAL occurred within the first month of illness between the two groups of 3.3% (12.4% vs 9.1%, odds ratio [OR] = 0.73 for the control arm and the experimental arm, respectively). With an α of 0.05 and a power of 0.8, a sample size of 1400 cases in each group will be needed. With an assumed dropout rate of 10%, a total of 3200 patients are planned for recruitment (1600 per arm).

4. Analysis Populations

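### SAP section 5.1.3 treats IVIG response, known only after prednisolone has started, like a baseline subgroup, so its stratum contrasts are not protected by randomization

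*SAP*

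**What the plan says.** Section 5.1.3 stratifies the primary-outcome GEE by age, gender, BMI group, "complete or incomplete KD, IVIG respond or not and CAL presence or not at baseline", and refers back to section 5.1.1 for the method. No caveat is attached to any factor.

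Section 3.3.1 fixes the timing. The experimental arm receives IVIG and aspirin "plus additional prednisolone 2 mg/kg per day in the initial treatment". Resistance is recurrent or persistent fever "after 36 hours of completion of initial IVIG infusion", and the infusion itself takes 12 to 24 hours.

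Two other places bear on the point. The Introduction says of poor response to IVIG, "which is commonly linked with higher risk of CAL". Section 2.1 makes the consequences of response into endpoints: "The secondary objectives include comparing the need of additional treatment or not and duration of fever after initial treatment". Section 2.2.2, item 6, ties additional treatment to resistance: "The acute KD patients in both arms resistant to the initial IVIG therapy will be given additional treatment". Section 5.2.1 then compares that need between arms.

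**The concern.** Every other factor in the list is settled before treatment, so randomization balances the arms within each level. IVIG response is settled after randomization and under the allocated drug. The SAP itself treats its consequence as something prednisolone may change.

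Suppose prednisolone turns some would-be non-responders into responders. The experimental non-responders are then only the hardest cases, while the control non-responders still include the convertible children. The experimental responders include converted children, whose counterparts in control are counted as non-responders. A treatment contrast within either stratum compares different kinds of child.

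The Introduction asks whether initial corticosteroid helps all patients or mainly those at higher risk of IVIG resistance. A row split by response is the one readers would turn to for an answer, and it cannot give one. Rescue therapy, which may include corticosteroid in either arm (sections 3.3.1 and 4.1), adds a further difference among non-responders.

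**Working it through.** **Plan's own figure.** The SAP gives no figure for this subgroup. Its sample size, used below for precision, reproduces. With 12.4% vs 9.1%, two-sided α 0.05 and power 0.80:

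n = [1.960·√(2·0.1075·0.8925) + 0.842·√(0.124·0.876 + 0.091·0.909)]² / 0.033² ≈ 1382 per group.

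Section 3.5 states "a sample size of 1400 cases in each group will be needed"; power at 1400 is 0.805.

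**Set-up.** Assume prednisolone makes no child resistant and has no effect on CAL in any child. There are three classes: always-responders (CAL risk pA), converted children who respond only with prednisolone (pC), and still-resistant children (pN). Non-response is rc in control and re in experimental. Differences are experimental minus control.

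- Non-responders: (rc − re)/rc × (pN − pC)
- Responders: (rc − re)/(1 − re) × (pC − pA)

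The true difference is 0 in every class.

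**Assumed inputs (none is in the SAP).** rc 15% or 20%; re 7.5% or 10%; pA 10%; pC 15% or 20%; pN 25% or 30%. This makes 16 combinations. Overall CAL comes out at 11.5–13.0%, in line with the SAP's 12.4% control rate.

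**Unadjusted results, percentage points.**

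- Non-responders, smallest: (15 − 10)/15 × (25 − 20) = +1.7
- Non-responders, largest: (20 − 7.5)/20 × (30 − 15) = +9.4
- Responders, smallest: (15 − 10)/90 × (15 − 10) = +0.3
- Responders, largest: (20 − 7.5)/92.5 × (20 − 10) = +1.4

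**Precision at 1400 per arm.** SE = √[pe(1 − pe)/ne + pc(1 − pc)/nc], where pe, pc are the stratum CAL risks and ne, nc the stratum sizes. In the largest non-responder case there are 105 experimental children at 30% and 280 control children at 20.6%, so SE = 5.08 points and the 95% half-width is 10.0. Over the grid, half-widths are 8.6–10.5 points in non-responders and 2.4–2.5 in responders. Every spurious difference in the grid is smaller than its half-width. The unadjusted chance of nominal significance is 6–45% in non-responders and 6–19% in responders, instead of 5%.

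**Boundary cases, unadjusted.**

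| Condition | Non-responders | Responders |
|---|---|---|
| Converted at always-responder risk (pC = pA) | +5.0 to +12.5 | 0 |
| Converted at still-resistant risk (pC = pN) | 0 | +0.8 to +2.7 |
| Non-response reduced by only 10% (relative) | +0.5 to +1.5 | +0.1 to +0.2 |
| No change in response | 0 | 0 |

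**With the planned covariate.** Section 5.1.1 includes "the mean of 5 coronary artery baseline z scores (described in section 2.2.1) as covariate variable". I approximated this by least squares of CAL on arm and baseline z at a single visit. Baseline z has SD 1, its mean rises from always-responders through converted to still-resistant children by a total gap s, and log odds of CAL rise 0.5 or 1.0 per SD within class.

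| Gap s | Non-responders | Responders |
|---|---|---|
| 0 | as unadjusted | as unadjusted |
| 0.5 SD | +0.4 to +8.0 | +0.2 to +1.2 |
| 1 SD | −1.5 to +6.5 | +0.05 to +1.0 |

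Adjustment removes part of the bias. In the strongest setting (1 SD, slope 1.0) it reverses the sign in non-responders in 4 of 16 combinations.

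**If prednisolone works.** Take rc 15%, re 5%, risks in the ratio 1:2:3, control CAL 12.4% overall, and a uniform risk ratio of 9.1/12.4 = 0.734. Then pA = 12.4/(0.85 + 0.10×2 + 0.05×3) = 10.3%. Control non-responders have 24.1%, and experimental non-responders 31.0% × 0.734 = 22.8%. The stratum shows −1.4 points, whereas the effect in still-resistant children is −8.3. The artefact can hide a benefit as well as mimic harm.

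**The case against.** The best case against giving this weight has four parts.

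- **The size is almost wholly assumed.** Only the 1400 per arm comes from the SAP; response rates, class risks and baseline gaps are illustrative. This stands. The document establishes that randomization does not protect the comparison, not how large the bias is.
- **The 6–45% false-positive range is unadjusted, while the plan adjusts for baseline z.** This also stands. In the adjusted single-visit model the range in non-responders is about 5–36% with a 0.5 SD gap and 5–26% with a 1 SD gap; in responders it is 5–16% and 5–13%. With no gap, adjustment does not help, and the upper ends are about 51% and 20%. These figures bracket the unadjusted ones and do not overturn them. The direction is likewise a clear excess only without adjustment.
- **The SAP does not call response a baseline factor;** its words at the end of the list attach to baseline CAL. True, but it handles response exactly as it handles the baseline factors.
- **Reach is limited.** This is one of six subgroup factors, no decision rule rests on it, and the non-responder estimate is imprecise. True, and it sets the severity, but an imprecise, biased row beside valid ones can still be misread.

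**Conclusion.** The point holds. As written, section 5.1.3 yields contrasts by IVIG response that are not randomized comparisons if prednisolone changes who responds. Bias then arises in non-responders when still-resistant and converted children differ in CAL risk, and in responders when converted children and always-responders differ. Each condition acts on its own stratum. In the unadjusted model there is no bias from this source if response is unchanged or if all three classes share the same risk.

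Under the main assumed grid the unadjusted artefact in non-responders is 1.7 to 9.4 points, which can exceed the 3.3-point overall effect the trial was sized for; in responders it is at most 1.4. The consequence is a potentially misleading estimate and an inflated false-positive rate, not a certain false finding. The primary ITT result and the sample size are untouched. This should be corrected, but it does not threaten the trial's main conclusion.

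**What to change.** Take IVIG response out of the list of baseline subgroups in section 5.1.3 and give it its own sentence. Section 5.1.1 describes the final analysis in the past tense, and the end of section 5.1.2.10 refers to work done during manuscript preparation and revision, so the item should not be silently deleted. State that it was listed, keep any result, and label it along these lines: *IVIG response is a post-randomization variable; results by response are descriptive and are not randomized treatment comparisons.* Draw no conclusion about effect modification from it. Compare response between arms as an outcome, as section 5.2.1 already does for need for additional treatment.

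The cost is a wording change and a footnote where the result is reported. The Table 3 shell shows only age, gender and BMI, so it needs no edit. Clinicians lose a causal reading of this row, which it could not support.

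A subgroup by resistance risk predicted from pre-treatment variables is optional and not needed to resolve the point. The SAP defines no score or cut-off, both would be chosen with results known, and section 5.3 plans imputation only for covariates with under 5% missing. If added, it must be labelled post hoc, with the score, the cut-off and the completeness of its inputs reported.
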